11.3. Ancillary Objectives

Ancillary Objective #1

Characterize the patient population that declines indicated IPG therapy.

Endpoint Definition

Decision to receive/decline therapy & why or why not

Analysis Methods

A. Statistical Methodology

Descriptive statistics will be used to describe the number of subjects that receive or decline an indicated therapy split by the reasons subjects provide for their decision.

B. Determination of Patients/Data for Analysis

Subjects in either study phase who receive a diagnosis of SND will be characterized. The subjects will be asked for their reasons to either receive or decline indicated therapy.

Ancillary Objective #2

Characterize the usage and impact of interventional tools (e.g., diagnostic algorithm(s), patient education tools) on the management of SND.

Endpoint Definition

Use of diagnostic tools; use of patient education materials, use of diagnostic algorithm(s), use of other tools

Analysis Methods

A. Statistical Methodology

Descriptive statistics will be used to describe the frequency of usage of interventional tools that assist in the diagnosis and management of SND.

B. Determination of Patients/Data for Analysis

Subjects in Phase II will be characterized. For each subject, the education tools provided to the subject and the interventional tools used by the patient's physicians that are applicable will be recorded.

Ancillary Objective #3

Evaluate device pacing mode of subjects receiving indicated IPG device before and after intervention

Endpoint Definition

Change in pacing mode set at time of implant

Analysis Methods

Statistical Methodology

Descriptive statistics will be used to describe the pacing mode implemented by implanting physicians.

Determination of Patients/Data for Analysis

Subjects in either study phase who receive indicated therapy for SND will be characterized. The device pacing mode set by the implanting physician will be recorded on the Implant CRF at the time of implant.

Ancillary Objective #4

Characterize the impact of the intervention on screening strategies and the impact on enrollment.

Endpoint Definition

Change in the proportion of subjects enrolled out of those screened by site

Analysis Methods**A. Statistical Methodology**

Descriptive statistics will be used to describe the proportion of subjects enrolled out of those screened per site.

B. Determination of Patients/Data for Analysis

All subjects screened and enrolled in each study phase.

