4.1. Study Objectives

Primary Objectives

1. Evaluate the impact of the intervention on the diagnosis of SND
2. Evaluate the impact of the intervention on SND subjects receiving a referral for an indicated IPG device

Secondary Objective

The secondary objectives to be measured include:

1. Evaluate the impact of the intervention on whether SND subjects undergo an IPG implant

Ancillary Objectives

1. Characterize the patient population that declines indicated IPG therapy
2. Characterize the usage and impact of interventional tools (e.g., diagnostic algorithm(s), patient education tools) on the management of SND
3. Evaluate device pacing mode of subjects receiving indicated IPG device before and after intervention
4. Characterize the impact of the intervention on screening strategies and the impact on enrollment.

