5.2. Data Collection

Table 1 depicts the data collection requirements for the study.

Table 1: Data Collection and Study Procedure Requirements at Subject Visits

Study procedure	Enrollment Baseline	Diagnostic Assessment	Implant
Informed Consent/ Medical release	X		
Inclusion / Exclusion	X		
Demographics	X		
Medical History	X		
Symptoms	X		
Vitals (HR, BP)	X		
Cardiovascular Medications	X	X	X
Diagnostic tests/ results	X if applicable	X	
Final Diagnosis		X	
Device Indication		X	
System information			X
Pt Education tool used (Phase II only)		X	
Treatment decision		X	
Death	As they occur		
Reason for exit			

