5.4. Diagnostic Assessment Visit(s)

A diagnostic assessment is any post enrollment visit to the study center for continued diagnostic assessment or management. During these visits information about utilization of diagnostic tests, results and cardiovascular medication use will be collected. Information about the final diagnosis and treatment decision will also be collected during the diagnostic assessment visit. The diagnostic assessment visit data will be complete:

- When the subject meets study exit criteria
- 6 months after the last Phase I enrollment for Phase I subjects
- 6 months after the last Phase II enrollment for Phase II subjects
- Patient education tools have been reviewed with the patient by the investigator (Phase II only)

The study protocol does not dictate when the Diagnostic Assessment(s) is/are to occur.

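### Ancillary Objective #2 promises the impact of the tools on SND management, but its endpoint, method and population give only Phase II usage, and no objective compares the diagnostic work-up between phases

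*Combined protocol and SAP*

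**What the plan says.** Section 4.1 lists the objective, and Section 11.3 repeats it in full: "Characterize the usage and impact of interventional tools (e.g., diagnostic algorithm(s), patient education tools) on the management of SND". It has two parts, usage and impact. The implementing text in Section 11.3 then reads:

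- Endpoint: "Use of diagnostic tools; use of patient education materials, use of diagnostic algorithm(s), use of other tools".
- Method: "Descriptive statistics will be used to describe the frequency of usage of interventional tools that assist in the diagnosis and management of SND".
- Population: "Subjects in Phase II will be characterized".

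Ancillary Objective #3, in the same section, draws on both phases: "Subjects in either study phase who receive indicated therapy for SND will be characterized". Ancillary Objectives #1 and #4 also cover both.

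On data collection, Section 5.4 says of the diagnostic assessment visits: "During these visits information about utilization of diagnostic tests, results and cardiovascular medication use will be collected". It attaches no phase restriction to this. Table 1 in Section 5.2 has a row for diagnostic tests and results, also unrestricted. The row that carries a restriction is the patient education tool: "Pt Education tool used (Phase II only)". Section 4.3 describes Phase I as the control period and confirms that its diagnostic assessment data are collected until 6 months after the last enrollment.

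**The concern.** An objective that asks about impact needs something that could change and something to compare it with. Ancillary Objective #2 specifies neither: it has no management variable, no Phase I comparator, and no contrast of users with non-users. Followed exactly, the plan yields a table of tool use and leaves half of the objective unanswered.

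The practical loss is in interpretation. Primary Objective #1 will show whether the proportion diagnosed with SND changes. If it rises, a reader will want to know whether testing also changed. If it does not, a reader will want to know whether testing stayed the same or changed without more diagnoses. The data for a descriptive answer are already to be collected in both phases, but no prespecified analysis uses them that way.

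**Working it through.** The point rests on the text. Ancillary Objective #2 states no figure to reproduce.

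**Step 1. Objective against implementation.**

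| Element | Usage | Impact |
|---|---|---|
| Objective (4.1, 11.3) | yes | yes |
| Endpoint (11.3) | yes | none named |
| Method (11.3) | frequency | no comparison |
| Population (11.3) | Phase II | no comparator |

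Three elements cause the gap, not one. Adding Phase I subjects alone would not close it, because the endpoint and method would still describe use only.

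**Step 2. What other objectives compare between phases.** Primary Objective #1 covers SND diagnosis and Primary Objective #2 covers referral (Section 11.1). The secondary objective covers implant and type of therapy (Section 11.2). Ancillary Objective #3 covers pacing mode, and Ancillary Objective #4 the share enrolled of those screened (Section 11.3). None takes the use of diagnostic tests as its endpoint.

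**Step 3. Whether the data exist.** Sections 4.3, 5.2 (Table 1) and 5.4 together show that test use and results are collected in Phase I and Phase II.

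**Step 4. Illustrative precision.** Inputs: about 200 subjects per phase (the evaluable number in Section 11.1) and assumed proportions tested, because the documents give none. Subjects are treated as independent.

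Half-width = 1.96 × √[p₁(1 − p₁)/n + p₂(1 − p₂)/n]

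- Assumed 40% vs 55%, n = 200: √(0.24/200 + 0.2475/200) = √0.0024375 = 0.0494; × 1.96 = 0.097, or 9.7 points.
- Same proportions, n = 210 (the minimum enrolled): √(0.4875/210) = 0.0482; × 1.96 = 0.094, or 9.4 points.
- Equal use in both phases, n = 200: 1.96 × √[2p(1 − p)/200] gives 5.9 points at 10%, 9.0 at 30% and 9.8 at 50%.

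Over these assumptions the half-width runs from about 6 to 10 points. The intervention is delivered by site, in up to 10 sites. If the change between phases differs from site to site, the true interval will be wider.

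**The case against.** The strongest reply is that this is a descriptive ancillary objective with one loose word, and that deleting the word would cure it. Impact on management is already compared between phases for the outcomes that matter most, no data are lost, and a comparison of testing could be specified later. A contrast between sequential phases also cannot isolate the tools, because it mixes the workshop, the algorithm, the patient materials, each site's adaptations and any time trend.

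Most of this stands, and it limits the point. Deleting the word would make the text consistent. It would also leave unplanned a comparison that the collected data can support, and one chosen after the results are known carries less weight. The attribution limit is real and should be stated in the plan.

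Four stronger readings are tempting, and the documents do not support them.

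- *The study cannot estimate impact at all.* It can, for the intervention as a whole, under the objectives listed in Step 2.
- *Restricting tool use to Phase II is itself an error.* It suits the usage half, because Section 4.3 gives sites the toolkit only after Phase I.
- *Use of the algorithm will not be captured because Table 1 has no row for it.* Section 11.3 requires the tools used by physicians to be recorded for each subject, and Appendix B says the case report forms were still being developed.
- *The algorithm is the plan's main mechanism and goes untested.* Section 4 names education, algorithms and documentation tools together, and Section 4.3 says only that the toolkit may include algorithms.

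**Conclusion.** The mismatch is real and minor. The analysis planned for Ancillary Objective #2 describes Phase II tool use and gives no estimate of impact, and no objective compares the diagnostic work-up between phases although the data are to be collected in both. No primary or secondary conclusion depends on it.

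A descriptive between-phase difference would have a 95% half-width of about 10 points at 40% vs 55% with 200 per phase. That figure rests on assumed proportions and on independence, so it shows only that the estimate could be informative. It would describe the whole intervention together with any time trend.

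**What to change.** Amend the endpoint, method and population of Ancillary Objective #2 together.

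- **Usage.** Keep the frequency of tool use, in Phase II subjects.
- **Work-up.** Add, for both phases, the proportion of enrolled subjects with each type of diagnostic test recorded within 6 months of enrollment. This matches the first time point of Primary Objective #1. A fixed window is needed because Section 5.4 does not dictate visit timing and ends collection 6 months after the last enrollment in each phase, so individual follow-up varies. State how tests entered at baseline, which Table 1 collects only if applicable, are counted.
- **Comparison.** Report Phase II minus Phase I, overall and by site, with a 95% CI that allows for site. Label it descriptive.
- **Interpretation.** State that the difference reflects the whole intervention and any time trend, and cannot be attributed to an individual tool.

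A Table 1 row for the algorithm and other tools would be a useful clarification, but it is secondary.

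The cost is a few lines of text and a little more analysis. No additional subjects, visits or test data are needed. The downside is an estimate that cannot be assigned to a single tool. If the sponsor does not want the comparison, the minimum is to remove impact from the objective.

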12. DATA AND QUALITY MANAGEMENT

Data will be collected using an electronic data management system for clinical trials. CRF data will be stored in a secure, password-protected database which will be backed up nightly. Data will be reviewed using programmed and manual data checks. Data queries will be made available to centers for resolution. Study management reports may be generated to monitor data quality and study progress. At the end of the study, the data will be frozen and will be retained indefinitely by Medtronic.

Procedures in the CIP require source documentation. In some cases, items on the CRFs may be considered source as long as there is evidence of the visit in the subject's record. Even when the CRF may be considered as source, an alternate method of source documentation is always strongly encouraged.

Save-to-disk data collected prior to discharge from the hospital will be sent to Medtronic, if available. Upon receipt, device data will be maintained with databases and retrieved for analysis and reporting.

The sponsor or a regulatory authority may audit the study center to evaluate the conduct of the study. The Clinical Investigator must immediately notify Medtronic when it learns that a regulatory authority will be auditing the site. The clinical investigator(s)/institution(s) shall allow trial related monitoring, audits, Ethics Board review, and regulatory inspection(s) by providing direct access to source data/documents.

13. WARRANTY/ INSURANCE INFORMATION

13.1. Warranty

Warranty information is provided in the product packaging for the commercially released system and additional copies are available upon request.

13.2. Insurance (Latin America)

Medtronic Latin America., Ltd. is a wholly owned subsidiary of Medtronic, Inc., which as the parent company of such entity maintains appropriate clinical trial liability insurance coverage as required under applicable laws and regulations and will comply with applicable local law and custom concerning specific insurance coverage. If required, a Clinical Trial insurance statement/certificate will be provided to the Ethics Committee/Institutional Review Board.

14. MONITORING

It is the responsibility of Medtronic to ensure proper monitoring of the study per regulations. Appropriately trained Medtronic personnel or delegates appointed by Medtronic will perform study monitoring at the study center in order to ensure that the study is conducted in accordance with the CIP the Clinical Trial Agreement (CTA), and applicable regulatory requirements. Medtronic must therefore be allowed access to the subjects' clinic and hospital records when so requested as per the Subject Informed Consent/Patient Data Release Consent, and CTA.

14.1. Monitoring Visits

Frequency of monitoring visits will occur based on subject enrollment, duration of the study, study compliance, findings from previous monitoring visits and any suspected inconsistency in data that requires investigation. Regulatory documents (e.g., IRB/MEC approval letters and CTAs, etc.) will be reviewed at a representative number of study centers. The number of centers and amount of subject data monitored against source documentation is determined by type of study and timing of data cutoff for study deadlines.

Monitoring visits will be conducted periodically to assess site study progress, the investigator's adherence to the CIP, regulatory compliance including but not limited to IRB/MEC approval and review of the study, maintenance of records and reports, and review of source documents against subject CRFs. Monitors facilitate site regulatory and study compliance by identifying findings of non-compliance and communicating those findings along with recommendations for preventative/corrective actions to site personnel. Communication with the site personnel occurs during the visit and following the visit via a written follow-up letter. Monitors may work with study personnel to determine appropriate corrective action recommendations and to identify trends within the study or at a particular center.

15. Required Records and Reports

The investigator is responsible for the preparation and retention of the records cited below. It is recommended that measures be taken to prevent accidental or early destruction of study related materials. All of the below records, with the exception of case history records and case report forms, should be kept in the Investigator Site File (i.e., the study binder provided to the investigator) or Subject Study Binder. CRFs may be maintained and signed electronically within the electronic data capture system during the trial. The following records are subject to inspection and must be retained for a period of two years (or longer as local law or hospital administration requires) after the date on which the investigation is terminated.

- All correspondence between the IRB/MEC, sponsor, monitor,
- Subject's case history records, including:
 - Signed and dated informed consent form/patient data release
 - Medical history
 - Baseline, diagnostic assessment(s), implant data, and scheduled follow-up
 - Documentation of the dates and rationale for any deviation from the protocol
- Signed and dated CRFs.
- All approved versions of the Clinical Investigation Plan, Patient Informed
- Consents/Patient Data Releases
- Lists of sites, investigators and IRB/MECs
- Signed and dated Clinical Trial Agreement
- Investigators current curriculum vitae (signed and dated, if required).
- Delegated task list.
- IRB/MEC approval documentation or a written waiver. Written information that the investigator or other study staff, when member of the IRB/MEC did not participate in the approval process (where applicable); IRB/MEC
- Roster of MEC members (when applicable).
- Study training records for site staff.
- Regulatory Authority Approval (if applicable)
- Insurance certificates (where applicable).
- Any other records that local regulatory agencies require to be maintained.
- Final Study Report including the statistical analysis.

15.1. Sponsor Records

Medtronic shall maintain the following accurate, complete, and current records:

- All essential correspondence which pertains to the investigation
- Signed Investigator Trial Agreements, and current investigator curriculum vitae (signed and dated, if required) , and delegated task list
- All signed and dated case report forms submitted by investigator, samples of informed consents, and other information provided to the subjects
- Copies of all IRB/MEC approval letters, IRB/MEC rosters and relevant
- IRB/MEC correspondence
- Names of the institutions, investigators and IRB/MEC's in which the clinical investigation will be conducted
- Correspondence with authorities as required by national legislation
- Insurance certificates, if applicable
- Names/contact addresses of monitors
- Statistical analyses and underlying supporting data
- Final report of the clinical investigation
- All approved versions of the Clinical Investigation Plan, PIC/PDR and study related reports
- Study training records for site personnel and Medtronic personnel involved in the study
- Any other records that local regulatory agencies require to be maintained.

Appendix A: Patient Informed Consent and Patient Data Release

At the time of Brady MX Clinical Investigation Plan Version 1 completion, the Patient Informed Consent and Patient Data Release form, that comply with local laws and regulations of Mexico were still being developed. A Patient Informed Consent and Patient Data Release Form will be distributed under separate cover.

Appendix B: Case Report Forms

At the time of Brady MX Clinical Investigation Plan Version 1 completion, case report forms were still being developed. Case Report Forms will be distributed under separate cover when available.

Appendix C: Preliminary Publication Plan

Publications addressing the Brady MX data will be handled according to Cardiac Rhythm Heart Failure Management Standard Operating Procedures and as indicated in the Clinical Trial Agreement.

Publication Committee

The Brady MX Advisory Committee will manage publications utilizing data from this study with the goal of publishing results. The Advisory Committee will develop the final Publication Plan as a separate document.

The Publication Committee's role is to manage elements addressed in the publication plan as outlined in this appendix, develop the final Publication Plan under separate cover, execute the Publication Plan, oversee the publication of primary, secondary and ancillary study results, review and prioritize publication proposals, provide input on publication content, and determine authorship. In addition, the committee will apply and reinforce the authorship guidelines set forth in the Publication Plan. Membership in the Publication Committee does not guarantee authorship. The committee will meet at regular intervals.

Management of Primary, Secondary and Ancillary Publications

The Publication Committee reviews all publications including primary, secondary and ancillary publications. Primary and secondary publications are those that address analyses of any or all primary objectives or secondary objectives, respectively, as specified in the Clinical Investigation Plan.

An ancillary publication is any publication that does not address the study objectives identified in the Clinical Investigation Plan. They include publications proposed and developed by other Medtronic departments or entities, clinicians participating in this clinical study and clinicians not participating in this clinical study. The committee will work with Medtronic to determine which ancillary publication proposals, if any, will be supported.

The committee may decide that no publications, including abstracts, will be published prior to the end of the study or with individual center data.

Requests for publications utilizing subset data (e.g., site) beyond the overall results will be evaluated for scientific validity and the ability of Medtronic to provide resources. The Advisory Committee must approve publication of ancillary requests and will ensure that requests do not present conflicts with other proposals and are not duplicative.

Criteria for Determining Authorship

Publications will adhere to authorship criteria defined by the International Committee of Medical Journal Editors (ICMJE, Uniform requirements for manuscripts submitted to biomedical journals, www.icmje.org). Individual authorship criteria defined by the target journal or conference will be followed when it differs from ICMJE criteria.

Authors, including Medtronic personnel, must at a minimum meet all of the conditions below:

- Substantial contribution to conception and design, or acquisition of data, or analysis and interpretation of data
- Drafting the article or revising it critically for important intellectual content
- Final approval of the version to be published

Decisions regarding authorship and contributor-ship will be made by the committee. The selected authors will be responsible for drafting the publication. All selected authors must fulfill the authorship conditions stated above to be listed as authors, and all contributors who fulfill the conditions must be listed as authors.

All investigators not listed as co-authors will be acknowledged as the “Medtronic Brady MX Clinical Study Investigators” and will be individually listed according to the guidelines of the applicable scientific journal. Any other contributors will be acknowledged by name and their specific contribution indicated.

Transparency

Transparency of study results will be maintained by the following means:

- A final report, describing the results of all objectives and analysis, will be distributed to all investigators, MECs in Mexico when required by local law
- Submitting for publication the primary study results after the trial ends
- Disclosing financial interests of the co-authors of publications according to the policies set forth by the corresponding journals and conferences
- Making an individual centers study data accessible to the corresponding investigator after the completion of the trial, if requested

